Mifepristone (MIFE), a competitive antagonist at the glucocorticoid receptor (GR), is FDA approved or under investigation for treatment of several endocrine and psychiatric disorders. Preclinical studies have shown that MIFE attenuates alcohol-induced mesolimbic DA neurotransmission in mice and reduces voluntary alcohol intake in rats. In alcohol dependent rodents, MIFE blocks the escalation of alcohol intake and compulsive drug-seeking responses during abstinence; it also reduces alcohol-withdrawal induced hyper-excitability and memory deficits. There is a single human study of MIFE for AUD treatment, showing MIFE reduces alcohol cue-induced craving in alcohol dependent subjects. Over time, MIFE should permit “healing” of dopaminergic neurotransmission and other drug-seeking circuitry dysregulated from excessive exposure to cortisol.

We are proposing a Phase I study of MIFE that examines safety, drug-drug interactions, and preliminary evidence of efficacy in reduction of alcohol effects. We will compare the effects of active and placebo MIFE on: 1) fMRI measures of functional connectivity (FC) and alcohol cue-induced brain activation (CA) focused on brain reward and stress pathways, 2) alcohol craving and withdrawal symptoms during alcohol abstinence on the CRU; 3) stress-induced alcohol motivated responding, and 4) alcohol sensitivity/reward. Also, using a within-subject design, we will assess changes in fMRI before and after MIFE administration. Subjects will receive up to 1200 mg MIFE or matching placebo daily over a 6 day period. Age-matched healthy control subjects will also undergo MIFE dosing over a 4 day period and fMRI procedures on an outpatient basis. We predict that MIFE treatment will decrease alcohol withdrawal

symptoms, alcohol motivated responding following stress and subjective experiences of high and positive alcohol effects compared to placebo.

2. Objectives (include all primary and secondary objectives)

Primary aim: The primary study objective is to determine MIFE effects in AUD and HC persons on a variety of alcohol-related measures. We will examine if there are significant interactions between MIFE treatment concurrent with alcohol administration by measuring subjective responses, adverse events and cardiovascular responses (heart rate (HR), blood pressure (BP)), compared to placebo. We also will examine MIFE effects on fMRI, alcohol withdrawal symptoms and craving, and alcohol motivated responding.

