Study Overview: This is a randomized, double-blind inpatient or outpatient human laboratory study. Procedures will be completed as a 7-day inpatient protocol in AUD subjects (N=75) and a 4-day outpatient protocol in an age and gender-matched comparison group of healthy control

(HC) subjects (N=75). On day 1, AUD subjects will be administered an alcohol beverage to control time from last drink before undergoing the first fMRI session. Two hours after alcohol administration, resting-state and alcohol-cued activity will be measured. Following the fMRI session on day 1, all subjects will be randomized to once-daily MIFE or placebo administration. They will also complete cognitive assessment tasks such as the Wisconsin Card Sorting Task (WCST) and two parts of the Wechsler Adult Intelligence Scale-III (WAIS-III), the digit span and the digit symbol substitution tests. They will receive their first medication dose on day 1. Over the next 3 days, AUD participants are monitored as they go through supervised alcohol withdrawal. On day 4, all subjects will complete a second fMRI session to quantify FC changes as a function of alcohol withdrawal and medication administration across key brain regions recently shown to be under GR regulatory control. They will also repeat cognitive assessment tasks. On day 5, AUD subjects complete the Trier Social Stress Test (TSST) followed by the Alcohol Motivated Response (AMR) procedure, during which subjects work for either their preferred alcohol beverage or money. On day 6, AUD subjects will participate in a cumulative alcohol administration procedure during which subjective and physiological responses to alcohol are repeatedly assessed. AUD subjects are discharged on day 7 after completion of the cognitive assessment tasks and a brief intervention. AUD participants are followed for two weeks post discharge. HC participants are followed for one week post second fMRI.

Table 1. Study Day	AUD Procedures	HC Procedures
Pre-admission	Assessment, Medical History, Vital Signs, blood work	Assessment, Medical History, Vital Signs, blood work
Day 1	Updated assessment, blood work, urine pregnancy test; alcohol administration and fMRI session 1 MIFE/placebo randomization and dosing; Cognitive Assessment	Updated assessment, blood work, urine pregnancy test; fMRI session 1 MIFE/placebo randomization and dosing; Cognitive Assessment
CRU stay	Days 2-6: Alcohol withdrawal monitoring	
MIFE/placebo dosing	Days 2-6	Days 2-4

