Day 4	fMRI session 2; Cognitive Assessment	fMRI session 2; Cognitive Assessment
Day 5	TSST and AMR	
Day 6	Alcohol sensitivity session	
Day 7	Cognitive Assessment; Discharge	
Day 11		OP safety follow-up visit
Day 14	OP safety follow-up visit	
Day 21	OP safety follow-up visit	

All visits will be completed remotely where possible (ex. Assessment and follow-up visits), although many procedures require in person assessment, including an inpatient stay for AUD participants. For all in-person visits, staff will use appropriate PPE (face mask/shield, gowns, gloves) and will practice physical distancing. Participants will be required to wear facemasks and if they do not have one, a facemask will be provided by our staff. Office spaces will be cleaned by sanitizing surfaces between office visits.

Assessment.

All potential subjects will be screened by telephone using a standardized initial questionnaire, which includes demography, drug and alcohol use patterns and associated problems, and a brief personal medical and mental health status. This telephone screen addresses the major inclusion/exclusion criteria for the study and quickly rules out respondents

who disqualify. We typically telephone screen 5 persons for each participant scheduled for in-person assessment.

Subjects who appear eligible based on phone screen will be invited to provide written informed consent. Teleconsent will be used as opposed to in person consenting where possible to reduce unnecessary in person encounters specifically for a consent procedure.

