MIFE has a rapid onset of action and achieves peak plasma levels within 1 - 2 hrs of oral dosing. Peak plasma levels and bioavailability increase as a function of dose but are not directly proportional to dose. However, plasma concentrations of MIFE metabolites do increase in direct proportion to dose; metabolites have antiglucocorticoid activity and contribute to long-acting drug effects (Pomara et al., 2002). MIFE is effective with once-a-day dosing. The half-life is 40 hrs following a single dose and 84.6 hrs following multiple doses. Following discontinuation of MIFE, plasma levels are detectable for up to 2 weeks (Heikinheimo et al., 2003). For this study, we selected to use the high MIFE dose of 1200mg, based on recent clinical trials for other neuropsychiatric disorders associated with HPA-axis dysfunction, and that 1200 mg MIFE has been safely administered over extended periods (MIFE Investigator Brochure, Corcept Therapeutics). This study only exposes subjects to MIFE for up to 6 days. We are not planning to reduce MIFE dose during such a brief treatment period. If a subject experiences significant medication side-effects or any serious adverse event or if the participant declines to continue medication, then we will discontinue that participant from the study. It

should be noted that inpatient subjects are under continuous nursing observation throughout the CRU stay and thus adverse events can be identified and addressed rapidly. HC subjects will be instructed to call the study doctor if they have any adverse events. Subjects will be randomized to active MIFE and placebo on a 2:1 ratio.

In the proposed study, MIFE will be administered under an IND ([name] 124365). MIFE (300 mg) and matching placebo will be provided by Corcept Therapeutics, Menlo Park, CA. We will overencapsulate the medication and placebo as necessary. The Johns Hopkins Bayview Investigational Drug Services (IDS) will maintain the inventory and dispense the medication. MIFE absorption and elimination are not affected by age, body weight, BMI, race or sex (Mifepristone Investigator Brochure, Corcept Therapeutics).

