As shown in Figure 1, cumulative alcohol dosing procedures generate highly reproducible BALs and subjective effects, with little between-subject variability. Subjective effects track BAL across the ascending and descending limb of the curve. Using this procedure, we have shown that the GABRA2 gene influenced alcohol subjective and physiological effects (Uhart et al., 2013). To date, we have completed this procedure over 150 subjects.

[figure not shown]

Figure 1. Time course of BAL and self-rated effects on the VAS and SHAS. Arrows indicate times of placebo

(P) and each alcohol drink (A1, A2, A3) consumed.

Discharge and Follow-up:

AUD subjects are discharged on day 7 following cognitive assessment and participation in a brief motivational intervention for alcohol use; information on treatment availability will be provided prior to discharge from the CRU. Under the supervision of [name], the intervention is delivered by Master's-level staff following procedures outlined in NIAAA Clinician Guide to Brief Intervention.

All female participants are advised to use nonhormonal birth control (e.g., condoms) for the duration of a one month period following discharge. All male participants will also be advised to use condoms for the duration of the follow-up visits and for at least 5 half-lives of the drug plus 90-days after the last dose of mifepristone. All subjects will be given a supply of condoms.

AUD subjects return weekly for 2 follow-up visits. HC subjects return one week post-second fMRI for a follow-up visit. As described above, MIFE is a long acting compound; plasma levels will likely remain elevated throughout the first two weeks post-discharge at the time of the follow-up visits. At each follow-up visit, participants provide self-reported alcohol use using TLFB procedures for the period since they were last seen, complete self-report measures of alcohol craving (as listed under the inpatient stay), medication side effects (SAFTEE) and adverse events. In addition, we will obtain a blood spot for PEth determination as a biomarker of recent drinking intensity. We also will get a blood sample for MIFE level and, at week 1 follow-up, a sample will be obtained to test for potassium level. Subjects will be reminded of the importance of use of nonhormonal birth control and/or condoms and will be provided with condoms.

b. Study duration and number of study visits required of research participants.

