Each subject will participate in an initial assessment, and a possible second assessment visit for completion of medical history, vital signs and laboratory tests. AUD participants will be admitted to the CRU for 6 nights. HC participants, who participate in the study on an outpatient basis, will continue MIFE dosing and salivary sample collection at home. For AUD participants, there are two follow-up visits at 1 and 2 weeks following CRU discharge. For HC participants, there is one follow-up visit at 1 week following the second fMRI. It is anticipated that subjects will complete all study procedures within a 6 month period.

c. Blinding, including justification for blinding or not blinding the trial, if applicable.

Staff and subjects will be blind to the alcohol and MIFE doses administered during this study to reduce expectancy effects.

d. Justification of why participants will not receive routine care or will have current therapy stopped.

Subjects are not seeking treatment for their AUD; they will not currently be engaged in therapy.

e. Justification for inclusion of a placebo or non-treatment group.

A placebo MIFE dose is included for comparison with the active drug effects and to control for expectancy effects.

f. Definition of treatment failure or participant removal criteria.

A participant will be removed from the study if s/he experiences a moderate or severe adverse event, is noncompliant with study or CRU rules, or if it is determined by the study physician to be unsafe to continue.

g. Description of what happens to participants receiving therapy when study ends or if a participant's participation in the study ends prematurely.

MIFE dosing is discontinued at the time of discharge from the study.

5. Inclusion/Exclusion Criteria

Healthy, non-treatment seeking, 21-60 years old, male and female subjects will be recruited through the media. Recruitment uses a mix of newspaper, radio, and on-line advertisements. Based on the 2011 census, the Baltimore metropolitan area is mostly Caucasian (61%) or African-American (30%); the remaining 9% is Asian (4%) and persons reporting two or more races (5%); 8.8% of the population report Hispanic ethnicity.

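### After Day 11, seven days after the last dose, adverse events in healthy controls are no longer actively asked about, although the plan says drug is detectable for up to two weeks.

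*Combined protocol and SAP*

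**What the plan says.** The HC schedule is consistent throughout Section 4.

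- **Dosing.** The introductory summary says "Age-matched healthy control subjects will also undergo MIFE dosing over a 4 day period". Table 1 gives the HC doses after Day 1 as Days 2-4, so the last dose is on Day 4. The Study Overview puts the second scan on the same day: "On day 4, all subjects will complete a second fMRI session".
- **Follow-up.** The Study Overview says "HC participants are followed for one week post second fMRI". Discharge and Follow-up repeats it ("HC subjects return one week post-second fMRI for a follow-up visit"), as does Section 4b: "For HC participants, there is one follow-up visit at 1 week following the second fMRI". Table 1 places this visit on Day 11. Nothing is scheduled for HC afterwards.
- **Exposure after stopping.** Section 4a, MIFE Administration, says "Following discontinuation of MIFE, plasma levels are detectable for up to 2 weeks". Discharge and Follow-up adds that "plasma levels will likely remain elevated throughout the first two weeks post-discharge at the time of the follow-up visits".
- **AUD comparison.** AUD participants are dosed to Day 6 and seen on Days 14 and 21.
- **Use of the data.** Adverse events and side effects head the list of primary outcomes in Section 7a. Specific aim 5 covers both cohorts. The Aim 5 analysis in Section 7c is a negative binomial regression on the number of events, with no mention of observation time.

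**The concern.** The plan gives its own period over which drug may still be present. The AUD visits span that period and the HC visit reaches only its midpoint, with no reason given.

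HC matter for the safety question because they receive MIFE or placebo without alcohol withdrawal or study drinking. Up to Day 11 they are asked about events with a structured instrument. After that, an event is known only if the participant calls. This applies to vaginal bleeding, which Section 8c lists as an event of special interest, and to any use of the dexamethasone that HC take home under Section 8b. Structured questioning and spontaneous reporting are not equivalent ways of finding events.

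There is also an analysis issue. Event counts from people observed for different lengths of time are not comparable unless the model allows for it, and Section 7c does not say that it will.

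**Working it through.** **1. HC on active drug.** Inputs: 75 HC (Section 5) and 2:1 allocation (Section 4a, MIFE Administration). 75 × 2/3 = 50 on MIFE and 75 × 1/3 = 25 on placebo. This reproduces the 50 versus 25 that Section 7c, Aim 4, states for an AUD cohort of the same size.

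**2. Time from last dose to last visit.**
- HC: Day 11 − Day 4 = 7 days.
- AUD: Day 14 − Day 6 = 8 days and Day 21 − Day 6 = 15 days.
- Stated detectability window: up to 14 days. HC coverage is 7/14, or half.
- Uncovered time on MIFE: 50 × 7 = 350 person-days, before dropout.

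**3. Drug remaining.** The documents give no decay model. Assuming first-order elimination, the fraction left is 0.5^(t / half-life), with t = 168 h at 7 days and 336 h at 14 days.

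| Half-life | Source | 7 days | 14 days |
|---|---|---|---|
| 84.6 h (multiple dose) | Section 4a | 25.2% | 6.4% |
| 40 h (single dose) | Section 4a | 5.4% | 0.30% |
| 18 h | Section 8a | 0.16% | under 0.001% |

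The 18 h figure is in active use. Section 8a supplies condoms to men for at least 94 days, and 5 × 18 h = 3.75 days, plus 90 = 93.75 days. With 84.6 h the same formula gives 17.6 + 90 = 107.6 days. The two sections therefore conflict, and the level at Day 11 spans about 0.2% to 25%.

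**4. What could be missed.** The documents give no late-event rate, so the risks below are assumptions. For risk p over Days 12-18 in 50 people, the expected number is 50p and the chance of at least one event is 1 − (1 − p)^50.

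| Assumed p | Expected events | Chance of at least one |
|---|---|---|
| 1% | 0.5 | 39% |
| 2% | 1.0 | 64% |
| 5% | 2.5 | 92% |
| 10% | 5.0 | 99% |

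**5. Observation time in Aim 5.** Counting from Day 1 to the last scheduled visit, HC contribute 11 days and AUD 21. With the same daily event rate in both cohorts, time alone would make AUD counts 21/11 = 1.9 times HC counts.

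Between treatment arms the schedule is balanced if 2:1 holds in each cohort and nobody drops out. Mean time on MIFE is (50 × 21 + 50 × 11)/100 = 16 days, and on placebo (25 × 21 + 25 × 11)/50 = 16 days. Unequal time therefore distorts cohort differences. It affects the treatment contrast only through unequal allocation or incomplete follow-up.

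**The case against.** Much of the case against has force.

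- **Late events are not simply lost.** A reader might infer that events after Day 11 go unrecorded. The documents do not support that. HC are told to call the study doctor about any adverse event (Section 4a). Section 8b tells participants to report adrenal symptoms and women to report unexplained bleeding. None of these instructions has an end date. What stops is active enquiry.
- **Day 11 is not the only safety contact.** HC have SAFTEE and the adrenal questionnaire by video on Days 2 and 3, a visit on Day 4 and daily checks while on drug. The gap is only after Day 11.
- **The randomised comparison is not biased.** It is tempting to say that harm is under-reported in the HC comparison. Both HC arms have the same follow-up, so the contrast is like for like over its window; only its scope is shorter.
- **Residual drug is not harm.** Detectable does not mean active. Section 8b reports no adrenal-insufficiency events in over 1500 people treated for one to two weeks. Quoting only the 25% figure would ignore the 18 h half-life.
- **Different schedules can be justified.** AUD participants take more doses, go through withdrawal, receive alcohol and provide drinking outcomes after discharge. The sentence on levels staying elevated is worded for discharge, which strictly applies to AUD alone.
- **Aim 5 states no AUD-versus-HC contrast.** It compares the two treatment groups.

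All of this stands and limits the point. It does not remove it: the general statement on two-week detectability is not confined to AUD, adverse events are a primary outcome in both cohorts, and passive reporting is weaker ascertainment.

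**Conclusion.** The point holds as a modest gap in safety ascertainment. For the second 7 days of a window of up to 14 days, events in about 50 MIFE-treated HC rest on spontaneous report. The consequences are lost late-event information and unequal cohort observation time (11 versus 21 days) in a count model with no stated offset. No sample size or power figure is affected, and the MIFE-placebo comparison within HC is not biased by it.

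The conclusion rests on the plan's own detectability statement and visit days, not on any half-life. How much exposure remains at Day 11 is unsettled, between about 0.2% and 25% under first-order decay. The number of late events is unknown; the figures above only show the range under assumed risks.

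**What to change.** 1. Add one remote SAFTEE and adverse-event contact for HC about two weeks after the last dose (around Day 18: 4 + 14). It should also record adrenal-insufficiency symptoms, vaginal bleeding and whether the take-home dexamethasone was used. Section 4a already provides the route: "All visits will be completed remotely where possible (ex. Assessment and follow-up visits". This is data collection only; it sets no dose, treatment or stopping rule.
2. If this is not done, state under Aim 5 that HC safety conclusions cover only the 7 days after the last dose.
3. In either case, account for observation time in the Aim 5 negative binomial model, for example with the log of days from first dose to last adverse-event enquiry as an offset. This is still needed after item 1, since 18 days would stand against 21.
4. Reconcile the half-lives in Section 4a (40 and 84.6 h) and Section 8a (18 h).

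The cost is one short call per HC participant by existing staff, a small added burden and some loss to contact. Items 2 to 4 need wording only, unless reconciling the half-lives alters the periods calculated from them.
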